[name] (investigator) has conducted several NIH-NIA funded measurement burst studies (57) and is currently conducting an NIH-NIA funded R01 (The ESCAPE [Effects of Stress on Cognitive Aging, Physiology, and Emotion] Study) and P01 measurement burst study in the Bronx (The Einstein Aging Study). The ESCAPE study uses smartphones to conduct ambulatory assessments of cognitive function, health behaviors, stress and emotional status in a diverse probability sample (N=304) that has been drawn from the same neighborhoods and resemble the proposed sample in terms of socioeconomic (i.e. education & income) status, age (up to 65) and racial diversity and literacy. Despite the duration and intensity of measurements (14 days, 5 times per day), participants have exhibited excellent compliance, completing over 80% of the smartphone assessments, and excellent retention over a 1 year follow-up (12% attrition) (58). Given that the proposed study utilizes a less demanding assessment protocol, we expect similar levels of compliance and retention. Ambulatory cognitive testing by smartphones in naturalistic settings is reliable and valid: as part of ESCAPE, [name] developed and validated smartphone-based cognitive tests of memory and processing speed in a diverse sample (58). This study used a sample that will resemble the proposed sample in terms of age (up to 65 yr), race and other demographics. Participants were prompted at 5 quasi-random times per day for 14 days to complete brief visuospatial working memory (Dot “Grid” Memory) and processing speed (Symbol Search) tasks on study-provided smartphones. These tasks are described in detail in section 2c2. Scores for each person were calculated by taking their average performance across all assessments. Reliability for the average scores was 0.97 and 0.98 for the Grid Memory and Symbol Search, respectively. Figure 1 illustrates construct validity of the smartphone-based ambulatory cognitive tasks, which were designed to measure visuospatial working memory (Grid Memory) and processing speed (Symbol Search). Both tasks had high factor loadings (>0.60) on their target constructs.

Recruitment & Retention Experience at Einstein: WHI, HCHS/SOL & ESCAPE:

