Randomization occurs after the baseline visit and body measurements when participants are judged to be eligible to proceed to study activities. Stratified permuted block randomization with variable block sizes will be used to randomize participants to one of the two study arms in a 1:1 ratio. Randomization will be stratified on sex, age (<53 yr, 53-65 yr), and education level (no more than high school or equivalent, more than high school), for a total of 8 stratification factors.

Statistical Analysis Plan

Analysis of the Primary Outcome

The primary outcome is a global composite cognition score assessed at 9 months post baseline. The primary outcome will be calculated as a Z-score composite measure of three ambulatory cognitive tasks, each administered up to 35 times, during each measurement burst: Symbol Search, Grid Memory, and Color Shapes. For a given cognitive task (“domain”), an outcome score is calculated for each of up to 35 sessions which are administered over a 1-week measurement burst, approximately 5 sessions per day (administered throughout the day in 5 target ~2 hour windows). For each Burst, and each of the 3 domains, the assigned Z-score is derived from their burst-average response for that domain, and then the three domain burst-average Z-scores are averaged for that Burst to create the primary composite outcome. Note that the Symbol Search and Dot Memory Z-scores **must be multiplied by -1** before creating the composite score because lower scores are better for these tasks. Thus, an increase in the composite score represents better cognitive performance.

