The primary analysis will be a between-arm comparison of the change from baseline in global composite cognition score, measured at Burst 2 (approximately month 9) as estimated from the ANCOVA regression model, which also includes adjustment for the stratification factors $Strat_i$ = (sex, age, years of education):

$$Z_{i2} = \beta_0 + \beta_1 Z_{i1} + \beta_2 Arm_i + \beta_3^T Strat_i + e_i.$$

In this model, age and years of education are treated as continuous. The stratification variables are added to assure proper confidence interval width, since randomization included stratification involving these variables (Kahan and Morris 2011). The coefficient β_2 quantifies the difference between treatment arms at Burst 2, adjusted for the baseline Burst 1 composite score measure and stratification variables, and will be fit using linear regression.

A supportive analysis of the primary endpoint will be the adjusted analysis examining the treatment effect on the change from baseline at Burst 2 for each of the three individual task domain scores \bar{Y}_{i2}^d .

Analysis of Secondary Outcomes

We will consider the treatment effect on the individual tasks (symbol search, color shapes and grid memory) in a longitudinal session-level model with the post-baseline session level outcome Y_{ijk}^d ($j>1$) regressed on the baseline average $Y_{i1.}^d$, treatment arm, time since baseline $time_{ij}$, time of day t_{ijk} (continuous covariate 0-24, centered at group average), day of week (i.e work day or day off), season (4 level factor variable: winter, spring, summer, fall), practice effects $g(s_{ijk})$ as a function of s_{ijk} (session number 1-35 as a continuous covariate), and, fatigue (visual

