Imputation Models for the Ambulatory Cognitive Scores

For the primary analysis, we will use the multiple imputation chained equation approach (MICE) to impute the necessary missing data to allow an ITT analysis (Azur et al. 2011). Burst measures that had fewer than 18 valid sessions for a given domain average (i.e. for \bar{Y}_{ij}^d for $d=1,2,3$; $j=1,2$) or a Burst 2 measure that started outside the Burst 2 window will be treated as missing and imputed.

A sequence of chained equations for MICE will be considered using: all variables in the primary analysis model (i.e., Arm, gender (0=female, 1=male), age at Burst 1, years of education, Burst 1 composite Z-score, and Burst 2 composite Z-score), run-in average variables for each of the tasks 1-3 in the composite outcome (\bar{Y}_{i0}^d), (averaging first 10 or fewer for each), MOCA score, indicator for in-person vs telephone MOCA, and interaction between these two MOCA variables, domain-specific Zscores based on the average of the available data from up to the first 10 sessions at Burst 1 for each of the three tasks 1-3 in the composite outcome, and the Burst 2 domain-specific Zscores using up to the first 10 sessions for each of the three tasks. Additional models may be considered as sensitivity analyses.

The imputation will be conducted in R using the `mice` package defaults for each variable type (e.g., predictive mean matching for the missing continuous variables (Van Buuren 2018). The number of multiple imputations will be greater than 25 (large enough to be stable, in terms of the intervention effect estimates and p-values).

Missing data approach for the secondary outcomes

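### The primary ANCOVA is valid but leaves out the pre-randomisation run-in scores that the SAP already prepares; adding one run-in composite is a small, nearly free gain in precision

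*SAP*

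**What the plan says.** Under Analysis of the Primary Outcome, the SAP regresses the Burst 2 composite on the Burst 1 composite, arm, sex, age and years of education, with the arm effect read off "as estimated from the ANCOVA regression model, which also includes adjustment for the stratification factors". The composite is an equal-weight mean: "then the three domain burst-average Z-scores are averaged for that Burst to create the primary composite outcome".

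Under Imputation Models for the Ambulatory Cognitive Scores, the list of imputation variables includes "run-in average variables for each of the tasks 1-3 in the composite outcome", each averaged over at most the first 10 sessions. These averages appear nowhere in the primary model.

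Protocol 10.3.3 makes completion of about 80% of run-in assessments (9 of 12 accepted) a condition of entry, so nearly everyone randomised should have run-in scores. Every description of the sequence (Protocol 4.3 and 6.2.3; SAP, Randomization) puts the run-in before randomisation.

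**The concern.** Run-in scores are earlier measurements of the same three tasks that make up the outcome. By listing them for imputation, the SAP already treats them as informative about the Burst 2 score. As imputation variables they help only where data are missing. In a trial whose planned randomisation was cut from 326 to 277 (Protocol 9.2), any variance they explain is precision left unused on the single primary comparison.

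**Working it through.** **1. The plan's own figure.** Protocol 9.2 gives 80% power with 125 per arm for 0.35 SD of change. At two-sided alpha 0.05 (assumed; neither document states it): Φ(0.35 × √(125/2) − 1.96) = Φ(2.767 − 1.960) = 79%. The absolute differences reproduce as 0.35 × √(2(1 − r)) = 0.157, 0.192 and 0.350 at r = 0.90, 0.85 and 0.5, against the stated 0.16, 0.19 and 0.35. That calculation uses the change score. For the same absolute differences, the planned ANCOVA gives 81%, 82% and 89%.

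**2. Measurement noise.** Protocol 2.2.3 reports, from 5 prompts a day for 14 days (70 sessions): "Reliability for the average scores was 0.97 and 0.98 for the Grid Memory and Symbol Search, respectively". By Spearman-Brown, R_m = R / (R + (1 − R) × 70/m):
- R = 0.97 becomes 0.942 at 35 sessions and 0.822 at 10
- R = 0.98 becomes 0.961 at 35 and 0.875 at 10

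Assumed, because the documents are silent: Color Shapes reliability 0.90 to 0.97 at 70 sessions, true correlation between tasks 0.2 to 0.6, independent session errors, tasks equally stable.

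**3. One case in full** (slow drift, r = 0.90, Color Shapes 0.97, task correlation 0.2, each Burst 1 domain score with variance 1).
- Error variance of the Burst 1 composite: (0.0392 + 0.0583 + 0.0583)/9 = 0.0173. True variance 0.4424; total 0.4597.
- Error variance of the run-in composite: 0.0173 × 35/10 = 0.0606.
- Residual variance given Burst 1 only: 0.4597 × (1 − 0.90²) = 0.0873.
- Under drift the run-in and Burst 1 measure the same level. Pooled error: 1/(1/0.0173 + 1/0.0606) = 0.0135. Variance of the pooled score: 0.4559.
- Residual variance given both: 0.45974 − (0.90 × 0.45974)²/0.4559 = 0.0842.
- Ratio: 0.0842/0.0873 = 0.964. The planned model has 6 coefficients, so residual degrees of freedom fall from 244 to 243. Net ratio: 0.964 × 244/243 = 0.968, a 3.2% reduction.

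**4. The range.** Net reduction in the variance of the arm effect from one run-in composite, n=250, over the assumptions in step 2:

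| Burst-to-burst correlation (Protocol 9.2) | Slow drift | Occasion-to-occasion fluctuation |
|---|---|---|
| 0.90 | 1.9 to 6.2% | 11 to 17% |
| 0.85 | 1.0 to 3.6% | 13 to 17% |
| 0.5 | −0.2 to 0.1% | 9 to 10% |

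With 80% completion applied to both studies (56, 28 and about 9 sessions), the top of the drift range at 0.90 becomes 6.8%.

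**5. Learning in the run-in.** A shift common to everyone has no effect. Person-specific learning acts as extra noise. If it adds 10 to 20% of the true variance to the run-in score, the reductions fall to 0.4 to 4.6% (drift, 0.90), 0.1 to 2.7% (drift, 0.85) and 7 to 13% (fluctuation, 0.85 to 0.90).

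**6. Power.** Dividing 2.767 by √(1 − g) gives 79.4% at g = 1% and 81.8% at g = 7%. Starting from exactly 80%, the figures are 80.4% and 82.8%. In participants, 250/(1 − g) − 250 is about 3 to 19.

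**The case against.** The planned ANCOVA is prespecified, unbiased and gives a valid interval, and not using every available predictor is a choice. That stands. It also stands that the size of the gain cannot be read from the documents, that the run-in is participants' first practice with the tasks, and that a change made this late (Protocol section 3 reports 260 participants at Visit 2) is acceptable only if it is fixed before unblinding.

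The objection that the net gain may be near zero stands for drift with a correlation of 0.5 and for drift with strong person-specific learning. It does not stand across the scenarios at 0.85 to 0.90, because a single composite costs one coefficient, about 0.4% of variance.

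Three stronger readings are tempting, and the documents do not support them.

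- **Splitting Burst 1 into three domain scores also narrows the interval.** The domain scores already enter through their mean. With equally stable and similarly reliable tasks, splitting widens the interval by about 0.4%. A clear gain (width ratio 0.94 to 0.99) needs markedly unequal stability, and the documents give no stability by task.
- **Coding the actual strata narrows the interval.** "Randomization will be stratified on sex, age (<53 yr, 53-65 yr), and education level", whereas in the analysis "In this model, age and years of education are treated as continuous". In 1,500 simulated trials with permuted blocks in the 8 cells, replacing the continuous terms by the cells gave width ratios of 0.999 to 1.013; adding the cells on top gave 1.003 to 1.004. The SAP's stated reason, "The stratification variables are added to assure proper confidence interval width, since randomization included stratification involving these variables", is a matter of matching analysis to design, and the continuous terms carry most of that information. A sentence of explanation would do.
- **Entering everything gains more.** Three domain scores, three run-in scores and two strata indicators add seven coefficients. That costs 244/237 = 1.030, or 3% of variance, which can use up most of a drift-type gain.

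A reader might also infer that Burst 1 is not a true baseline, since Protocol section 3 puts the burst week after the clinic visit and 6.2.3 has the assignment received at Clinic Visit 1. The documents do not settle that order, and this point does not depend on it. It is a further reason to value the run-in scores, and the SAP should state the sequence.

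**Conclusion.** This is an improvement on offer, not a flaw. The primary estimate, its interval and the power statement remain valid as written. One run-in composite would lower the variance of the arm effect by about 1 to 7% under slow drift at the correlations the protocol considers likely (0.85 to 0.90), and by more if bursts fluctuate by occasion. Drift is the cautious case, because a run-in held shortly before Burst 1 may share its fluctuations. The size rests on the assumed Color Shapes reliability, task correlations, equal task stability and independent session errors; run-in learning reduces it. Since the run-in precedes randomisation, adjusting for it cannot bias the arm comparison. The gain does not extend to separate domain scores or strata indicators.

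**What to change.** Before unblinding, add one covariate to the primary model: a run-in composite formed from the three run-in task averages, using the same Burst 1 means and SDs and the same signs as the Burst 1 composite. Keep the currently specified model as a sensitivity analysis. If arm-level results have already been seen, reverse the two roles.

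The cost is one coefficient and a sentence or two in the SAP. No new data are needed. The imputation list already contains the three run-in averages, so the few missing values are covered and the imputation model stays compatible with the analysis model. Add a sentence explaining why age and education enter as continuous terms.

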analogue). A b-spline with 3 degrees of freedom will be used to model a non-linear practice effect and the likelihood ratio test will be used to assess whether non-linear terms for the practice effect are needed. Splines will also be used to fit a circadian rhythm curve for the effect of the time of day of the session $f(t_{ijk})$. For the continuous tasks (grid memory and symbol search), linear mixed effects model will be fit with a random intercept to account for the correlation of repeated measures within an individual (Model 1). Random intercept variances are allowed to vary by burst. We will also consider whether there is evidence for between person variation in the change over time by including random slope terms for the time effects (Model 2). The treatment effect in Models 1 and 2 will be modeled with a main effect an interaction with the continuous time variable. Thus, the following linear mixed effects models will be fit for each continuous domain:

Model 1: Longitudinal linear mixed effects model for repeated measures across burst and session.

$$Y_{ijk}^d = \beta_0 + \beta_1 Y_{i1}^d + \beta_2 \text{Arm}_i + \beta_3 \text{time}_{ij} + \beta_4 \text{Arm} * \text{time}_{ij} + \sum_l \beta_{5l} f(t_{ijk}) + \beta_6 \text{Day}_{ijk} + \beta_5' \text{Season}_{ij} + \sum_m \beta_{8m} g(s_{ijk}) + \beta_9 \text{Fatigue}_{ijk} + \tilde{\beta}_{10}^T \text{Strat}_i + b_{ij} + e_{ijk},$$

Model 2: Longitudinal linear linear mixed effects model for repeated measures across burst and session, including random effects for both slope and intercept.

$$Y_{ijk}^d = \beta_0 + \beta_1 Y_{i0}^d + \beta_2 \text{Arm}_i + \beta_3 \text{time}_{ij} + \beta_4 \text{Arm} * \text{time}_{ij} + \sum_l \beta_{5l} f(t_{ijk}) + \beta_6 \text{Day}_{ijk} + \beta_7' \text{Season}_{ij} + \sum_m \beta_{8m} g(s_{ijk}) + \beta_9 \text{Fatigue}_{ijk} + \tilde{\beta}_{10}^T \text{Strat}_i + b_3 \text{time}_{ij} + b_4 \text{Arm} * \text{time}_{ij} + b_{ij} + e_{ijk},$$

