where b_{ij} is the person level effect (random intercept term) for participant i and Burst j , and e_{ijk} is the residual error term assumed to be mean 0, independent across time and individuals and approximately normally distributed. In this model, response Y_{ijk}^d is modeled as a function of the overall baseline level and the term β_4 summarizes the potential treatment effect on the change over time. Models will be further adjusted for age, gender, APOE4 allele, race, and ethnicity in supportive analyses. The difference in time and underlying cognitive function within a burst is assumed negligible, thus the time and season variables in these models will be determined by the first day of the Burst.

The Color Shapes task has only 7 possible values, so a similar generalized estimating equation (GEE) approach will be taken using the Poisson mean model and robust sandwich variance for the number of incorrect responses (0-6).

Our secondary outcomes also include between arm comparisons of MHD-related dietary intake based on self-report and biomarker measures of intake at 9 months post baseline. Outcome models of between-arm differences in dietary intakes indicative of the MHD as measured by nutritional biomarkers, and self-report at Burst 2 will be conducted in a similar manner to the models specified above for the primary cognitive outcomes: namely, ANCOVA models that adjust for the baseline level, Arm and stratification factors will be fit. Tocopherols and carotenoids plasma biomarkers will be additionally adjusted for cholesterol variables per Gross et al (2003). Longitudinal models considering ASA24 data across the 4 bursts will be fit using similar mixed effects models, simplified to analyze only the Burst level average for the ASA24 dietary intakes (no repeated measures within a burst). Analyses will generally be complete case

analyses for the dietary variables. Energy adjustment will be considered where appropriate. Sensitivity analyses with additional adjustment variables associated with missing, as well as exploratory analyses that examine potentially differences in intervention effect by gender, race, ethnicity and age, will also be considered.

The plasma biomarkers include: total folate, alpha and gamma tocopherol, carotenoids (alpha carotene, beta carotene, zeaxanthin+lutein, beta cryptoxanthin, and vitamin B12), lycopene, and fatty acid profile. Serum sodium is an additional secondary outcome, indicative of hydration.

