Self-reported dietary outcomes indicative of the MHD diet include the DII score, which is derived from the self-reported data as both unadjusted and unadjusted for energy, water, and the following factors chosen because of hypothesized pro- or anti-inflammatory effects and because they were readily available summaries from the ASA24: total calories (KCAL), protein (PROT), total fat (TFAT), solid fats (SOLID_FATS), carbohydrates (CARB), total folate from food (FF), folate from non-food sources (non-FF), vitamin B12, carotenoids: retinol (RET), beta carotene (BCAR), alpha carotene (ACAR), cryptoxanthin (CRYP), lycopene (LYCO), Lutein+zeaxanthin (LZ); alpha tocopherol (ATOC), fatty acids (EPA, DPA, DHA), total fruits (F_TOTAL), green leafy vegetables (V_DRKGR), beans and peas (V_LEGUMES), whole grains (G_WHOLE), cured meats (PF_CUREDMEAT), poultry (PF_POULT), seafood high in n-3 fatty acids (PF_SEAFD_HI), nuts and seeds (PF_NUTSD), cheese (D_CHEESE), and added sugars (ADD_SUGARS).

Exploratory Analyses

Exploratory outcomes include the treatment effect on the two exploratory tasks (Shopping List and Rotation Span), which will be evaluated with similar longitudinal models developed for the three domains that make up the primary composite Z score (namely Models 1 and 2). Shopping List will be modeled with a linear mixed effects model. Due to the concern of departure in the Rotation Span scores from normality (a slight truncation), this domain will be modeled with generalized estimating equation with robust variance estimate.

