For randomized trials, under the MAR assumption and when only the outcome variable is missing, complete case analyses that additionally adjust for all the variables related to the missingness imputation will be consistent and can be the most efficient analysis (Little et al, 2022). Thus for the secondary endpoints, the adjustment approach will be considered. For the repeated measures models of the cognitive outcomes, the proposed adjusted analysis models are as described above (Model 1 and Model 2). For the dietary biomarker and self-reported ASA-24 outcomes, adjustment for baseline demographics (age at Burst 1, gender, race, ethnicity, years of education, MOCA score, indicator for in-person vs telephone MOCA, and interaction between the two MOCA variables, and BMI. Energy adjustment will be considered as appropriate for the dietary component. In particular, parsimonious outcome models that include adjustment of variables when found to be associated with missingness will be considered. Analysis of tocopherols and carotenoids plasma biomarkers will be additionally adjusted for cholesterol variables per Gross et al (2003).

References

Van Buuren, S. (2018). *Flexible imputation of missing data.* CRC press.

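### Models 1 and 2 adjust the arm comparison for fatigue measured after randomisation, with no version without it, so they may not give the total effect of assignment

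*SAP*

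**What the plan says.** Under Analysis of Secondary Outcomes, the SAP sets out to estimate the treatment effect on Symbol Search, Color Shapes and Grid Memory from post-baseline sessions only (j>1). The covariates are the baseline average, arm, time since baseline, time of day, day type, season and practice. The list ends with "session number 1-35 as a continuous covariate), and, fatigue (visual" analogue scale. Both model equations carry a term beta_9 x Fatigue_ijk beside Arm and Arm x time.

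The arm terms are presented as the treatment effect: "The treatment effect in Models 1 and 2 will be modeled with a main effect an interaction with the continuous time variable". The SAP adds that beta_4 "summarizes the potential treatment effect on the change over time". It does not say that either term is conditional on fatigue. The only listed variants add covariates (age, gender, APOE4, race, ethnicity); none removes fatigue.

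Two other sets of analyses follow the same pattern. For Color Shapes, "a similar generalized estimating equation (GEE) approach will be taken using the Poisson mean model". The exploratory tasks are covered by a clause, "which will be evaluated with similar longitudinal models developed for the three domains that make up the primary composite Z score".

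One task-level analysis, applied to all three tasks, lists no fatigue term: "A supportive analysis of the primary endpoint will be the adjusted analysis examining the treatment effect on the change from baseline at Burst 2".

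**The concern.** A covariate measured after randomisation can itself be changed by the intervention. Protocol section 7 lists increased energy among the benefits participants may notice, so fatigue during follow-up is a plausible consequence of assignment. If it is one, beta_2 and beta_4 omit the part of the effect that passes through fatigue. They can also be biased by unmeasured common causes of fatigue and cognition.

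The SAP treats other possible mediators differently. Dietary components and weight loss are taken up in separate exploratory mediation analyses and are not entered in the treatment-effect model.

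The session-level model is the first analysis under secondary outcomes and the only specified arm comparison of cognition at months 18 and 27. A reader could take its arm terms as the total effect of the diet. Comparing them with the Burst 2 task analysis would not show the problem, because the two also differ in outcome level, time scale and other covariates. Only the same session-level model fitted with and without fatigue would show it.

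The SAP states intention-to-treat only for the primary outcome. The issue is therefore what the secondary treatment effect means, not a breach of a stated rule.

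**Working it through.** The plan gives no figure on this point, and the documents give neither beta_9 nor an arm difference in fatigue. Everything below marked *assumed* is illustrative. Scores are in between-person SDs of one task, with higher meaning better.

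**1. Shift caused by adjustment**

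At burst j, unadjusted minus adjusted arm contrast = beta_9 x D_j, where D_j is the diet-minus-comparison difference in fatigue. Assume beta_9 = -0.10 per SD of fatigue.

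| Assumed D at months 9, 18, 27 | Change in contrast on adjusting | Change in beta_4 per 9 months |
|---|---|---|
| 0, 0, 0 | 0 | 0 |
| -0.3, -0.3, -0.3 | -0.03 at each burst | 0 |
| -0.3, -0.2, -0.1 | -0.03, -0.02, -0.01 | +0.01 |
| +0.3, +0.3, +0.3 | +0.03 at each burst | 0 |

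A stable difference moves beta_2, and one that changes over time also moves beta_4. The SAP counts time from baseline, so in the waning case beta_2 itself, read at time zero, would shift by -0.03 - 0.01 = -0.04.

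A simulation agrees. It used 250 participants, three follow-up bursts of 35 sessions with 20% missed, 200 replicates and time centred at month 9. Adjusted minus unadjusted was:
- no fatigue difference: beta_2 -0.0005;
- constant difference: beta_2 -0.029, beta_4 0.000;
- waning difference: beta_2 -0.031, beta_4 +0.010.

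Monte Carlo standard errors were 0.0007 (beta_2) and 0.0003 (beta_4).

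**2. Bias from dropping fatigue if missed sessions depend on it**

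Bias of the fatigue-free contrast = beta_9 x (observed D - full D). Assumed: fatigue SD 1, 80% of sessions completed overall, missingness logistic in fatigue.

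| Full D | Log-odds of missing per SD of fatigue (comparison, diet) | Observed D | Bias |
|---|---|---|---|
| -0.3 | 0.5, 0.5 | -0.289 | -0.0011 |
| -0.3 | 1.0, 1.0 | -0.267 | -0.0033 |
| -0.3 | 0.2, 0.8 | -0.400 | +0.0100 |
| -0.3 | 0.8, 0.2 | -0.179 | -0.0121 |
| 0 | equal in both arms | 0 | 0 |
| 0 | 0.2 and 0.8, either order | ∓0.117 | ±0.0117 |

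**3. Precision lost by dropping fatigue**

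- Protocol section 2.2.3 gives reliabilities R of 0.97 (Grid Memory) and 0.98 (Symbol Search), from 14 days x 5 = 70 scheduled sessions with over 80% completed, so n = 56 to 70.
- Session-to-person variance ratio = n(1-R)/R: 1.73 to 2.16 for Grid Memory, 1.14 to 1.43 for Symbol Search.
- Section 9.2 gives a burst-to-burst correlation of about 0.90, so burst-mean variance given baseline = 1 - 0.90² = 0.19.
- Session level: sqrt(1 + ratio x r²/(m x 0.19)), with fatigue assumed to explain r² = 1 to 10% of session variance. For m = 28 (80% of 35) the SE rises 0.1 to 2.0%. For m = 18 (the SAP's minimum for a valid burst) it rises up to 3.1%.
- Burst level: 1/sqrt(1-q), with q = 5 to 10% assumed, gives 2.6 to 5.4%.
- Both at 10%, with the upper variance ratio: sqrt(1/(1-q) + ratio x r²/(m x 0.19)) gives 7.3% (m = 28) and 8.4% (m = 18) for Grid Memory, and 6.7% and 7.4% for Symbol Search.

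**The case against.** The reach is narrow. The primary analysis has no fatigue term, the supportive Burst 2 analysis answers the 9-month domain question without one, and Protocol section 9.4 lists the 27-month associations as exploratory. This limits severity and stands.

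The only support in the documents for a diet effect on fatigue is one clause in the safety section. That is also true, so the size is open and may be zero.

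The strongest point is that the SAP gives these models a missing-data role. It argues that adjusting for predictors of missingness keeps complete-case analysis consistent under MAR, then says: "For the repeated measures models of the cognitive outcomes, the proposed adjusted analysis models are as described above (Model 1 and Model 2". Fatigue might be one such predictor, and a contrast net of momentary state is a legitimate estimand if it is labelled as one. However, the SAP never names fatigue as a predictor of missingness and never labels the arm terms as conditional. The adjustments it does spell out, for the dietary outcomes, begin "adjustment for baseline demographics (age at Burst 1, gender, race, ethnicity, years of education, MOCA score". Those are baseline variables, which leave the total effect intact. The missing-data argument is a reason to keep the adjusted fit alongside, not to have it alone.

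The extension to Color Shapes and the exploratory tasks rests on the word similar, so the covariates of those models also need stating.

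**Conclusion.** The concern holds. As written, Models 1 and 2 condition the arm terms on a post-randomisation variable that the protocol itself says the diet might improve, and no version without it is planned. The primary result and the Burst 2 task analysis are unaffected. The affected results are the session-level longitudinal ones at months 9 to 27, together with the Color Shapes and exploratory-task models if they carry the same covariates.

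The size cannot be derived from the documents. It is zero if assignment does not change fatigue. Under the assumed slope of -0.10 and a 0.3 SD arm difference it is 0.03 SD, in either direction. This should be changed, but it does not threaten the primary conclusion.

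**What to change.** Drop Fatigue_ijk from the main version of every model that reports a treatment effect: Models 1 and 2, the Color Shapes GEE and the exploratory-task analogues. Keep time of day, day type, season and session number. Retain the fatigue-adjusted fit as a sensitivity or mediation analysis, labelled as conditional on fatigue, and report both on the same sessions.

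Do not substitute mean Burst 1 fatigue as a baseline covariate unless it is confirmed to be collected before participants learn their assignment. Protocol section 6.2.3 has assignment received at Visit #1, ahead of the Burst 1 week. It also places randomisation after body measurements, which are scheduled separately, so the order needs confirming.

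State which survey supplies the fatigue value for each session. The SAP indexes fatigue by session, while Protocol section 3 describes it as a daily measure and places it in the bedtime survey. The questionnaires were not available to settle this.

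The cost is one extra fit per task and no new data. Under the assumptions above, the SE of the arm contrast rises by 0.1 to 3.1% (session level), 2.6 to 5.4% (burst level), or about 7 to 8% with both at their upper ends. If missed sessions depend on fatigue differently by arm, the main model carries a bias of about 0.01 SD. A gap between the two fits would not by itself separate mediation from missingness, so both should be shown and interpreted with that caution.
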